6.1.1.2 Serious Adverse Events

If an adverse event meets any of the following criteria, it is to be reported to AbbVie as a serious adverse event within 24 hours of the site being made aware of the serious adverse event:

Death of Subject	An event that results in the death of a subject.
Life-Threatening	An event that, in the opinion of the investigator, would have resulted in immediate fatality if medical intervention had not been taken. This does not include an event that would have been fatal if it had occurred in a more severe form.
Hospitalization or Prolongation of Hospitalization	An event that results in an admission to the hospital for any length of time or prolongs the subject's hospital stay. This does not include an emergency room visit or admission to an outpatient facility.
Congenital Anomaly	An anomaly detected at or after birth, or any anomaly that results in fetal loss.
Persistent or Significant Disability/Incapacity	An event that results in a condition that substantially interferes with the activities of daily living of a study subject. Disability is not intended to include experiences of relatively minor medical significance such as headache, nausea, vomiting, diarrhea, influenza, and accidental trauma (e.g., sprained ankle).
Important Medical Event Requiring Medical or Surgical Intervention to Prevent Serious Outcome	An important medical event that may not be immediately life-threatening or result in death or hospitalization, but based on medical judgment may jeopardize the subject and may require medical or surgical intervention to prevent any of the outcomes listed above (i.e., death of subject, life-threatening, hospitalization, prolongation of hospitalization, congenital anomaly, or persistent or significant disability/incapacity). Additionally, any elective or spontaneous abortion or stillbirth is considered an important medical event. Examples of such events include allergic bronchospasm requiring intensive treatment in an emergency room or at home, blood dyscrasias or convulsions that do not result in inpatient hospitalization, or the development of drug dependency or drug abuse.

For serious adverse events with the outcome of death, the date and cause of death will be recorded on the appropriate case report form.

6.1.2 Adverse Event Severity

The investigator will use the following definitions to rate the severity of each adverse event:

Mild	The adverse event is transient and easily tolerated by the subject.
Moderate	The adverse event causes the subject discomfort and interrupts the subject's usual activities.
Severe	The adverse event causes considerable interference with the subject's usual activities and may be incapacitating or life-threatening.

6.1.3 Relationship to Study Drug

The investigator will use the following definitions to assess the relationship of the adverse event to the use of study drug:

Reasonable Possibility	An adverse event where there is evidence to suggest a causal relationship between the study drug and the adverse event.
No Reasonable Possibility	An adverse event where there is no evidence to suggest a causal relationship between the study drug and the adverse event.

For causality assessments, events assessed as having a reasonable possibility of being related to the study drug will be considered "associated." Events assessed as having no reasonable possibility of being related to study drug will be considered "not associated." In addition, when the investigator has not reported a causality or deemed it not assessable, AbbVie will consider the event associated.

If an investigator's opinion of no reasonable possibility of being related to study drug is given, an Other cause of event must be provided by the investigator for the serious adverse event.

[figure not shown]
6.1.4 Adverse Event Collection Period

All adverse events reported from the time of Day -7 for subjects initiating TB prophylaxis during the screening period (if applicable) or from the time study drug administration until 70 days following discontinuation of study drug administration have elapsed will be collected, whether solicited or spontaneously reported by the subject. In addition, serious adverse events and protocol-related nonserious adverse events will be collected from the time the subject signed the study-specific informed consent.

All subjects who do not initiate adalimumab therapy not supplied in the context of the clinical trial after the end of study participation will have a follow-up phone call 70 days after the last administration of study drug to obtain information on any new or ongoing AEs.

Adverse event information will be collected as shown in [Figure 2](#).

Figure 2. Adverse Event Collection

* If the subject initiates TB prophylaxis during the Screening Period, AEs will be collected starting at the Day -7 visit. If the subject does not initiate TB prophylaxis during the Screening Period, AEs will be collected starting at Baseline (SAEs and nonserious protocol related AEs are collected starting at the time of consent).

6.1.5 Adverse Event Reporting

In the event of a SAE, and additionally, any nonserious event of malignancy in subjects 30 years of age or younger, whether associated with study drug or not, the Investigator will notify Clinical Pharmacovigilance within 24 hours of the site being made aware of the event by entering the SAE or nonserious event of malignancy in subjects 30 years of age and younger into the electronic data capture (EDC) system. Serious adverse events

and non-serious events of malignancy in subjects 30 years of age and younger that occur prior to the site having access to the RAVE[®] system or if RAVE is not operable should be documented on the SAE Non-CRF forms and emailed (preferred route) or faxed to Clinical Pharmacovigilance within 24 hours of being made aware of the serious adverse event.

For safety concerns, contact the Immunology Safety Team at:

Immunology Safety Team Hotline

In case of subject safety concerns or medical emergencies should the Primary Study Designated Physician be unavailable, please call the following central back-up number:

6.1.6 Pregnancy

Pregnancy in a study subject must be reported to AbbVie within 1 working day of the site becoming aware of the pregnancy. Subjects who become pregnant during the study must be discontinued (Section 5.4.1). Pregnancies will be collected from the date of the first dose through 150 days following the last dose of study drug.

Information regarding a pregnancy occurrence in a study subject and the outcome of the pregnancy will be collected.

Pregnancy in a study subject is not considered an adverse event. However, the medical outcome of an elective or spontaneous abortion, stillbirth or congenital anomaly is considered a serious adverse event and must be reported to AbbVie within 24 hours of the site becoming aware of the event.

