 - For subjects taking 6-MP, the dose should not exceed 1 mg/kg/day.
 - For subjects taking IM/SC MTX, dose should not exceed 25 mg per week.
 - Note: Oral MTX use is allowed during the study (at a stable dose for 28 days prior to Baseline), however use of oral MTX is not sufficient for inclusion into the study.

Note: If a subject is on both an oral corticosteroid and an immunosuppressant listed above, BOTH of the drugs need to meet the above criteria.

and/or

- Concurrent therapy with corticosteroids or the above-mentioned immunosuppressants (azathioprine, 6-MP or IM/SC MTX) is not required for subjects not currently taking these medications who were previously treated during the past 2 years and have confirmed documentation of failure to respond, or were previously treated during the past 5 years and have confirmed documentation indicating lack of tolerability.
5. Subject has a negative TB Screening Assessment. If the subject has evidence of a latent TB infection during the Screening Assessment, the subject must initiate and complete a minimum of 3 weeks (or per local guidelines, whichever is longer) of an ongoing TB prophylaxis prior to Baseline (Section 5.3.1).
 6. If female subject, is either not of childbearing potential, defined as postmenopausal for at least 1 year or surgically sterile (bilateral tubal ligation, bilateral oophorectomy and/or hysterectomy) or is of childbearing potential and is practicing an approved method of birth control throughout the study and for 150 days after last dose of study drug.

Examples of approved methods of birth control include the following (see local informed consent for more detail):
 - Condoms, sponge, foams, jellies, diaphragm or intrauterine device (IUD);
 - Hormonal contraceptives for 90 days prior to study drug administration;
 - A vasectomized partner.
 7. Subject must be able and willing to give written informed consent and to comply with the requirements of this study protocol.
 8. Subject is judged to be in otherwise good health as determined by the Principal Investigator (or designee) based upon the results of medical history, laboratory profile, physical examination, CXR, and a 12-lead electrocardiogram (ECG) performed during Screening.
 9. Subject must be able and willing to self-administer subcutaneous (SC) injections or have a qualified person available to administer SC injections.

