A final phone call will be made to the subject approximately 70 days after the last dose of study drug to determine the status of any ongoing AEs/SAEs or the occurrence of any new AEs/SAEs. The information will be recorded on the appropriate eCRF page. The 70-day follow-up phone call will not be required for any subject who initiates adalimumab therapy not supplied in the context of the clinical trial after the end of study participation.

All attempts must be made to determine the date of the last dose of study drug and the primary reason for premature discontinuation. The information will be recorded on the appropriate eCRF page.

For subjects who are considered lost to follow-up, reasonable attempts must be made to obtain information on the final status of the subject. At a minimum, two phone calls must be made and one certified letter must be sent.

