Appendix H. 70-Day Follow-Up Phone Call – Sample

Site Name/Number: _____

Subject Number: _____

Please contact subjects that discontinue adalimumab 70 days following study drug discontinuation.

Date of Call: _____

- Lost to Follow-Up. (Please check this box if subject was not willing to provide any follow-up information or you were unable to speak to the subject following at least one attempt.)
- No Events Reported.
- N/A subject continued adalimumab therapy after the end of their study participation.

List any Adverse Events (AE) and/or Serious Adverse Events (SAE) that occurred since the subject was last seen in clinic for this study. If needed, provide AE/SAE details on the AE worksheet attached. (Please report all SAEs to AbbVie within 24 hours of being made aware of the event.)

If events are listed above, your monitor will review and retrieve the appropriate eCRF pages during their next visit.

Please fax all completed forms to:

[Name] at XXX-XXX-XXXX

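### Pregnancies are to be collected to 150 days after the last dose, but no scheduled pregnancy check follows the Week 26/Premature Discontinuation visit and no scheduled contact covers Days 70 to 150

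*Protocol*

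**What the plan says.** Protocol Section 6.1.6 sets the collection window: "Pregnancies will be collected from the date of the first dose through 150 days following the last dose of study drug". Inclusion criterion 6 (Section 5.2.1) uses the same post-dose period for contraception, requiring a woman of childbearing potential to be "practicing an approved method of birth control throughout the study and for 150 days after last dose of study drug". The 150 days therefore look deliberate.

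Section 6.1.6 makes two further statements that matter here. First, "Pregnancy in a study subject is not considered an adverse event". Second, "the medical outcome of an elective or spontaneous abortion, stillbirth or congenital anomaly is considered a serious adverse event". The reporting duty depends on awareness: a pregnancy "must be reported to AbbVie within 1 working day of the site becoming aware of the pregnancy".

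The scheduled procedures after treatment are these:
- **Pregnancy test.** Table 1 (note m) and Section 5.3.1.1 place the last one, a urine test, at the Week 26/Premature Discontinuation visit.
- **Follow-up call.** Under Section 6.1.4, subjects who do not go on to non-study adalimumab "will have a follow-up phone call 70 days after the last administration of study drug to obtain information on any new or ongoing AEs". The sample form in Appendix H tells the site: "List any Adverse Events (AE) and/or Serious Adverse Events (SAE) that occurred since the subject was last seen in clinic for this study". It has no pregnancy item.
- **Waiver.** Section 5.4.1 adds: "The 70-day follow-up phone call will not be required for any subject who initiates adalimumab therapy" from outside the trial after study participation ends.

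No visit, call or test is scheduled after the Day 70 call.

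**The concern.** The protocol commits to collecting pregnancies over a period that its own schedule does not cover. A site that follows the plan and uses the sample form as printed does not ask any woman about an ongoing pregnancy after the Week 26/Premature Discontinuation visit. The Day 70 call asks about adverse events, and Section 6.1.6 takes pregnancy out of that category. Women who move to non-study adalimumab need not be called at all.

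What is at stake is safety ascertainment. If few or no exposed pregnancies are reported after treatment, the study report cannot tell whether few occurred or few were asked about.

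The two collection periods also do not fit together. Section 6.1.4 ends adverse event collection 70 days after study drug stops. Section 6.1.6 collects pregnancies to Day 150 and classes certain outcomes as serious adverse events. A pregnancy learned of on Day 100 is inside the pregnancy window, but a serious outcome of it falls outside the adverse event period.

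**Working it through.** **Inputs**
- Window: first dose to last dose + 150 days (Section 6.1.6).
- Last dose for a completer: Week 24, that is 24 × 7 = 168 days after the first dose; none at Week 26 (Section 5.3.1.1).
- Last pregnancy test: Week 26/Premature Discontinuation. For a completer this is (26 − 24) × 7 = 14 days after the last dose. For an early discontinuer the visit is due within 2 weeks of the last dose (Section 5.4.1).
- Last scheduled contact: the call at about Day 70 after the last dose (Sections 5.4.1 and 6.1.4).
- Screening: up to 35 days (Section 5.1).

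**The plan's own figure.** Section 5.1 gives a maximum duration of 39 weeks. Counting to the call, 35 + 168 + 70 = 273 days, and 273 / 7 = 39.0 weeks. This reproduces the stated figure and confirms that scheduled follow-up ends with the Day 70 call. Counting the 70 days from Week 26 instead gives (35 + 182 + 70) / 7 = 41.0 weeks, which does not match.

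**Post-dose part of the window (150 days)**
- After the last pregnancy test: 150 − 14 = 136 days; 136 / 150 = 91%.
- After the last scheduled contact: 150 − 70 = 80 days; 80 / 150 = 53%.
- For a subject exempt from the call, the last scheduled contact is the Week 26/Premature Discontinuation visit, so the 136-day figure applies to both.

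The 136 is approximate. The ±3-day visit window alone moves it between 133 and 139 days, and a discontinuation visit held sooner than 14 days after the last dose makes it longer.

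**Full window (first dose to last dose + 150 days).** Its length is the days from first to last dose, plus 150. The table assumes a discontinuation visit 14 days after the last dose.

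| Last dose | Window (days) | After the call: 80 / window | After the last test: 136 / window |
|---|---|---|---|
| Week 0 | 150 | 53% | 91% |
| Week 4 | 178 | 45% | 76% |
| Week 8 | 206 | 39% | 66% |
| Week 12 | 234 | 34% | 58% |
| Week 24 (completer) | 318 | 25% | 43% |

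**If a Day 150 contact were scheduled.** 35 + 168 + 150 = 353 days; 353 / 7 = 50.4 weeks, which is 80 days (11.4 weeks) beyond the stated 39 weeks.

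**The case against.** The strongest reply is that Section 6.1.6 is a reporting rule, triggered by site awareness, and not a visit schedule. A longer awareness-based period can sensibly sit beside a shorter adverse event period, and nothing stops a site from reporting a pregnancy on Day 120. This stands in part: collection after the last visit is permitted, and what is missing is scheduled ascertainment. It does not remove the point, because the text says pregnancies will be collected to Day 150 and does not say that this depends on unprompted reports.

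Four further points limit the concern:
- **Share of the window.** A reader might infer that most of the stated window is uncovered. The window opens at the first dose, so for a completer the gaps are 25% and 43% of it. The larger shares apply to the 150 post-dose days or, measured from the last test, to early discontinuers.
- **Outcomes.** A reader might infer that abortions, stillbirths and anomalies are caught only if volunteered. They are serious adverse events, and the Day 70 call asks about those. Unless the call is waived, such an outcome before Day 70 could surface there.
- **Numbers affected.** The documents do not give the number of women of childbearing potential. If 25% to 50% of 200 subjects is assumed, the result is 50 to 100 women at risk of going unasked. That is not a count of missed pregnancies, which contraception should make far fewer.
- **Form and consent.** Appendix H is a sample, and the consent text was not available for this review. It may tell women to report a pregnancy, so the absence of such advice cannot be claimed. Even so, Sections 5.4.1 and 6.1.4 also describe the call in terms of adverse events only.

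No planned result depends on this. The SAP specifies no pregnancy analysis, and its treatment-emergent period ends at 70 days (SAP Section 11.2.1).

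**Conclusion.** The point holds as a gap in scheduled ascertainment. No scheduled pregnancy check follows the Week 26/Premature Discontinuation visit, leaving about 136 of the 150 post-dose days. No scheduled contact covers Days 70 to 150, which is 80 of those 150 days and 25% of a completer's 318-day window. After the last visit, an ongoing pregnancy becomes known only if the site happens to hear of it.

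The completer figures assume a last dose at Week 24 and visits on their nominal days. They count scheduled contacts only; follow-up of an unresolved adverse event, or of a pregnancy already known, may bring contact after Day 70. The documents do not support a claim that the protocol forbids later reporting, or any estimate of how many pregnancies would be missed.

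**What to change.** 1. Add one pregnancy question for women of childbearing potential to the existing 70-day call, in Sections 5.4.1 and 6.1.4 and on the Appendix H form.
2. Reconcile Section 6.1.6 with Section 6.1.4 and the follow-up schedule. State that collection from Day 70 to Day 150 relies on spontaneous reports, unless the sponsor chooses to schedule a later contact. State also how a serious pregnancy outcome after Day 70 is handled, and what applies to subjects whose call is waived.

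The cost is one extra question on a call already planned, plus wording changes. A Day 150 contact is optional and costs more: it would lengthen the stated maximum duration from 39 to 50.4 weeks and require edits wherever that duration appears. The point does not depend on it.

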6.1.7 Toxicity Management

Subjects who develop a new infection while undergoing treatment with adalimumab should be monitored closely. Administration of study injections should be interrupted if a subject develops an infection requiring IV anti-infective treatment or if an infection meets the definition of "serious" (see Section 6.1.1 for definitions). Study medication may be restarted once the physician determines that the infection has been successfully treated. Otherwise prohibited concomitant medications may be given if medically necessary. Prior to use, every attempt should be made to contact the AbbVie Study Physician for direction on re-introduction of adalimumab therapy after prohibited medication administration.

If the subject must undergo elective surgery, the study injections must be interrupted 2 weeks prior to the surgery. If the subject must undergo emergency surgery, the study injections must be interrupted at the time of the surgery. The injectable study medication can recommence at least 2 weeks after surgery once the physician has examined the surgical site and determined that it has healed and there is no sign of infection.

6.2 Product Complaint

6.2.1 Definition

A Product Complaint is any Complaint (see Section 6.0 for the definition) related to the biologic or drug component of the product or to the medical device component(s).

For a product this may include, but is not limited to, damaged/broken product or packaging, product appearance whose color/markings do not match the labeling, labeling discrepancies/inadequacies in the labeling/instructions (example: printing illegible), missing components/product, device not working properly, or packaging issues.

For medical devices, a product complaint also includes all deaths of a patient using the device, any illness, injury, or adverse event in the proximity of the device, an adverse event that could be a result of using the device, any event needing medical or surgical intervention including hospitalization while using the device and use errors.

Any information available to help in the determination of causality by the device to the events outlined directly above should be captured.

6.2.2 Reporting

Product Complaints concerning the investigational product and/or device must be reported to the Sponsor within 24 hours of the study site's knowledge of the event via the Product Complaint form. Product Complaints occurring during the study will be followed-up to a satisfactory conclusion. All follow-up information is to be reported to the Sponsor (or an authorized representative) and documented in source as required by the Sponsor. Product

Complaints associated with adverse events will be reported in the study summary. All other complaints will be monitored on an ongoing basis.

Product Complaints may require return of the product with the alleged complaint condition (syringe). In instances where a return is requested, every effort should be made by the investigator to return the product within 30 days. If returns cannot be accommodated within 30 days, the site will need to provide justification and an estimated date of return.

The description of the complaint is important for AbbVie in order to enable AbbVie to investigate and determine if any corrective actions are required.

7.0 Protocol Deviations

AbbVie does not allow intentional/prospective deviations from the protocol unless when necessary to eliminate an immediate hazard to study subjects. The principal investigator is responsible for complying with all protocol requirements, and applicable global and local laws regarding protocol deviations. If a protocol deviation occurs (or is identified) after a subject has been enrolled, the principal investigator is responsible for notifying Independent Ethics Committee (IEC)/Independent Review Board (IRB) regulatory authorities (as applicable), and the following AbbVie Clinical Monitors:

Such contact must be made as soon as possible to permit a review by AbbVie to determine the impact of the deviation on the subject and/or the study.

For the purposes of this protocol, reportable deviations are defined as:

- Subject entered into the study even though she/he did not satisfy entry criteria
- Subject who developed withdrawal criteria during the study and was not withdrawn
- Subject who received wrong treatment or incorrect dose
- Subject who received excluded or prohibited concomitant treatment

